4.6.4. Protocol Deviation Resulting in Exclusion from the PPS

Protocol deviations will be classified as either significant or not. A list of protocol deviations resulting in exclusion from the PPS is provided in [Appendix C](#) of the SAP.

5. Subject Disposition

Disposition will be summarized for all enrolled subjects by dosage and overall. It will include the number and percentage of subjects in each analysis set (SS, ATS, and PPS). The number and percentage of subjects who have completed, are ongoing or discontinued from the study as well as reason for study discontinuation will be tabulated. Note that any set-specific summaries should be based on the subjects within that set.

The reason(s) for study discontinuation will be presented as a data listing and may include any of the following: withdrawal of consent, administrative decision by the investigator or the sponsor, ineligibility, significant protocol derivation, subject noncompliance, and AE.

6. Demographics and Baseline Characteristics

6.1. Demographics

Baseline demographic data to be evaluated will include age, sex, ethnicity, race, height and weight. Age will be calculated as the integer part of $(ICF\ Date - Birth\ Date + 1)/365.25$. All demographic and baseline characteristic data will be listed for each subject in the SS. No inferential statistics will be generated.

6.2. Medical History

Medical history will be presented as data listing. The listing will present all patients in the SS.

6.3. Hemophilia B History

Hemophilia B history will be presented as data listing. The documented FIX activity and number of bleeds in the past 12 months will be displayed by descriptive statistics.

The data listing will present year of diagnosis of Hemophilia B, start year of Hemophilia B therapy, family history of Hemophilia B, documented FIX activity, treatment type, number of bleeds in the past 12 months and treatment medicine information. The table and listing will present all patients in the SS.

6.4. Inclusion and Exclusion Criteria

All inclusion/exclusion information on enrolled subjects will be presented in a data listing. The listing will include the failed inclusion/exclusion criteria. A table summarizing the failed inclusion/exclusion criteria will be presented for enrolled subjects.

7. Treatments and Medications

7.1. Prior and Concomitant Medications

Medications will be coded using the World Health Organization Drug Dictionary (Version Sep 2015). If the start or end date of medications is missing, it will be imputed as shown in [Appendix A](#). If the start date is completely missing, and the end date of a medication is prior to the initiation of study treatment (Day 0), it will be counted as a prior medication. If the start date is completely missing, and the end date of a medication is after the initiation of study treatment (Day 0), it will be counted as a concomitant medication. If the end date is completely missing, it will be counted as a concomitant medication.

7.1.1 Prior Medications

Prior medications are defined as those medications with a recorded end date prior to the initiation of study treatment (Day 0). Prior medications will be presented as a data listing for all patients in SS.

7.1.2 Concomitant Medications

Concomitant medications are defined as those medications that are taken on or after the initiation of study treatment (Day 0).

Concomitant medications will be presented as a data listing for all patients in SS.

7.2. Drug Exposure

The duration of study participation will be summarized by dosage for all subjects. The duration of study participation (days) is calculated as the date of the last visit (as recorded on the Study Completion/Early Withdrawal page) minus date of the Day 0 visit plus 1. If the date of the last visit on the Study Completion/Early Withdrawal page is missing, or if a subject is lost to follow-up, the latest available visit date will be used. The duration of study participation for each subject will also be presented in a listing.

The SS will be used for all analyses defined above.

8. Efficacy Analysis

The primary efficacy endpoint is defined as the change from baseline in FIX activity at Week 6 as determined by aPTT. The EDA, through descriptive statistics and graphic method, will be performed on the primary efficacy endpoint.

The secondary efficacy endpoints include: ABR; and the annualized and average weekly FIX replacement therapy. All secondary efficacy endpoints will be presented in a listing at the scheduled time points for each subject and will be summarized by dosage at scheduled time points. No formal statistical inference will be performed for the secondary efficacy endpoints.

All efficacy analyses will be conducted on the ATS. Additionally, sensitivity analyses for the primary efficacy endpoint will be performed by utilizing the PPS; additional sensitivity analyses will be performed if necessary.

9. Safety Analysis

Safety evaluations will be based on the incidence, severity, type of AEs, clinically significant changes or abnormalities in the subject's vital signs, and clinical laboratory results.

All safety analyses will be conducted on the SS.

9.1. Adverse Events

Adverse event terms recorded by the clinical site will be mapped to PT using MedDRA, (version18.1). Severity/toxicity grade will be defined according to the NCI CTCAE v4.03.

An AE is defined as any untoward medical occurrence in a subject enrolled into this study (from the time the subject signs the ICF until their exit from the study) regardless of its causal relationship to study treatment. A TEAE is defined as any event not present before exposure to study product or any event already present that worsens in severity or increases in frequency after exposure to study product.

The relationship of TEAE to study product is categorized as “unrelated”, “possibly related”, “probably related”, or “definitely related”. For summaries by relationship, AEs with a missing relationship are considered to be “possibly related”. For summaries by CTCAE grade (grade 1, grade 2, grade 3, grade 4, and grade 5), AEs missing a CTCAE grade are considered to be CTCAE grade 3. If AE start date is missing, it will be imputed as shown in [Appendix A](#).

The overall number of TEAEs will be summarized for the following:

- All TEAE,
- All serious TEAEs,
- All TEAEs with grade ≥ 3
- All study product related TEAEs,
- All study product related TEAEs \geq grade 3,
- All study product related serious TEAEs,
- TEAEs leading to study discontinuation,
- Any TEAE leading to death.

The total number, the frequency, and the percentage of subjects with TEAEs will be tabulated by dosage, SOC, and PT for the following:

- TEAEs,
- Serious TEAEs,
- TEAEs by relationship,
- TEAEs resulting in study discontinuation,
- TEAEs by severity,
- Related TEAEs,
- Related serious TEAEs,
- TEAEs grade ≥ 3 ,
- All study product related TEAEs/Serious TEAEs (DLT) \geq grade 3.

At each level of summarization, a subject will be counted only once (with the strongest relationship and the greatest severity) for each TEAE he experiences within that level. Data listings will be provided for all TEAEs.

9.2. Death

All subjects who have an AE with an outcome of “Death” will be presented in a listing.

9.3. Clinical Laboratory Evaluations

Hematology, clinical chemistry, urinalysis, and some special laboratory data will be displayed for each scheduled assessment. Hematology will include complete blood count with differential. Clinical chemistry will include sodium, potassium, chloride, carbon dioxide, blood urea nitrogen, creatinine, glucose, calcium, phosphate, magnesium, albumin, total protein, creatinine kinase, bilirubin (total and indirect), alanine aminotransferase (ALT), aspartate aminotransferase, alkaline phosphatase, gamma-glutamyl transferase, and lactate dehydrogenase. Urinalysis will include specific gravity, pH, glucose, protein, blood (by dipstick), ketone (by dipstick), and microscopic examination (if blood or protein is found). Other laboratory parameters will include hepatitis B virus surface antigen, hepatitis C virus ribonucleic acid (RNA), and human immunodeficiency virus RNA, prothrombin time/international normalized ratio, fibrin degradation product (D-dimer), and aPTT.

Numeric hematology, clinical chemistry and urinalysis results will be presented in listings. Clinical chemistry is also summarized by dosage using standardized results and change from baseline. ALT will be provided as a separate listing to monitor the ALT level and its relationship with administration of prednisolone and change of FIX activity. A similar figure will also be presented.

9.4. Vital Sign Measurements

. All vital sign data, including heart rate, systolic blood pressure, diastolic blood pressure and respiratory rate for subjects in the SS, will be presented by-subject in a listing.

9.5. Electrocardiogram

ECG data will be presented in a data listing.

9.6. Factor IX Inhibitor

Samples will be collected at scheduled time points to monitor for an immune response to FIX. FIX inhibitor will be presented by-subject in a listing. FIX inhibitor will also be presented over time in a figure for each subject.

9.7. Neutralizing Antibodies to Adeno-Associated Virus rh10

Samples will be collected at scheduled time points to monitor for an immune response to AAVrh10. Antibodies to AAVrh10 will be presented by-subject in a listing. It will also be presented over time along with cell-mediated immune response in a figure for each subject.

9.8. Viral shedding

Saliva, urine, and stool will be collected at scheduled time points to monitor for the presence of shed virus. Viral shedding will be presented by-subject in a listing. It will also be presented over time in a figure for each subject.

9.9. Cell-mediated immune response

The presence of cytotoxic T lymphocytes specific for AAVrh10 and FIX will be determined by ELISPOT assay at scheduled time points. Cell-mediated immune response will be presented by subject in a listing.

9.10. Adeno-associated virus rh10 binding antibody IgG assay

Circulating anti-AAVrh10 antibodies will be determined by ELISA assay at scheduled time points. Circulating anti-AAVrh10 antibodies will be presented by subject in a listing. It will also be presented over time in a figure for each subject.

9.11. Factor IX genotyping

A listing will be provided for the subjects who provide the samples for genotyping.

10. Quality of Life (QoL) Analyses

Two questionnaires, EQ-5D-5L and Haem-A-QoL, will be collected at baseline, week 24, 36, 48, and 52. For EQ-5D-5L Listings will be presented for each questionnaire.

11. Pharmacodynamics

FIX activity, as measured by aPTT will be presented in a listing for each scheduled time points for each subject. FIX activity will be summarized by dosage at each scheduled time point. It will also be presented in a figure along with cell-mediated immune response for each subject. The association between FIX activity and dose will be evaluated by a linear mixed-effects regression model adjusted for potential confounders.

12. Statistical considerations for Data Safety Monitoring Committee (DSMC) meeting

DSMC members will meet after week 6 data from all subjects of a cohort is available. Dosage recommendation computed through bCRM along with necessary tables/listings/figures (denoted by * in the table of contents) will be prepared and presented.

13. Interim Analysis

An interim analysis will be conducted after week 6 FIX activity results are available for all enrolled subjects. All tables/listings/figures for the full analysis will be produced for interim analysis.

14. References

Braun TM. The bivariate continual reassessment method: extending the CRM to phase I trials of two competing outcomes. *Control Clin Trial.* 2002;23:240-56.

White GC 2nd, Rosendaal F, Aledort LM, et al. Definitions in hemophilia. Recommendation of the scientific subcommittee on factor VIII and factor IX of the scientific and standardization committee of the International Society on Thrombosis and Haemostasis.

Tessella 2005. Simulation Test Results. Bivariate Continuous Reassessment Method.

15. Appendices

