3.2.3 Prophylactic Factor IX Washout Periods

3.2.3.1 Screening Period

If the subject does not have a documented history of FIX activity, a blood sample will be needed to confirm the severity of hemophilia B for inclusion ([Section 4.1](#)) after washout of recombinant FIX ([Figure 3–2](#)). For subjects taking long-acting recombinant FIX prophylactically to prevent bleeding episodes, the washout period is to start at approximately Day –29 and last for 21 days (approximately Day –8). For subjects taking traditional recombinant FIX prophylactically to prevent bleeding episodes, the washout period is to start at approximately Day –29 and last for 7 days (approximately Day –22). The blood sample must be obtained and results available prior to dosing on Day 0. Subjects can then transition

back onto their prophylactic regimen until the washout period during the treatment period (prior to Week 6) is to begin ([Section 3.2.3.2](#)).

NOTE: This washout period is not needed for subjects with a documented history of FIX activity.

Figure 3–2**Recombinant FIX Washout During the Screening Period**

Abbreviations: FIX, factor IX.

[figure not shown]
- a. Washout required for subjects that do not have a documented history of FIX activity to meet eligibility criterion (ie, $\leq 2\%$ of normal).
- b. Following assessment of FIX activity, subjects can transition back on to their prophylactic regimen until the protocol mandated washout period prior to the Week 6 assessment of FIX activity.

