3.2.3.2 Treatment Period

In order to accurately assess vector-derived FIX activity as a result of DTX101 infusion, subjects will stop taking FIX prophylactically prior to the assessment of peak FIX activity at Week 6 and transition to an on-demand regimen for the remainder of the study. Subjects prophylactically using traditional recombinant FIX will be asked to begin the washout period starting at Week 5. Due to the longer half-life, subjects prophylactically taking long-acting recombinant FIX (eg, Alprolix) will be asked to begin the washout period starting at Week 3 ([Figure 3–3](#)).

If, at any time during the study, a subject experiences bleeding episodes frequent enough to consider prophylactic treatment, the investigator will discuss treatment options with the medical monitor. If a subject resumes prophylactic FIX replacement therapy, as rescue treatment after Week 6, additional washout periods prior to Week 24 and Week 52 will also be performed. Subjects prophylactically using traditional recombinant FIX will be asked to begin the washout period starting at Week 23 and Week 51. Due to the longer half-life, subjects taking long-acting recombinant FIX (eg, Alprolix) will be asked to begin the washout period starting at Week 21 and Week 49 (Figure 3–3).

Figure 3–3 Recombinant FIX Washout During the Treatment Period

Abbreviations: FIX, factor IX.

- a. Following washout, subjects will be transitioned to an on-demand regimen for the remainder of the study.
- b. Washout needed if, at any time during the study after Week 6, a subject experiences bleeding episodes frequent enough to consider re-initiating prophylactic treatment.

The on-demand use of recombinant FIX is not prohibited and may be used at any time during the study. Subjects will be asked to record this use as outlined in [Section 8.1.3](#).

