4.2. Analysis Visits

Due to subjects potentially returning outside of the scheduled visits, visit windows will be defined for by-visit summary and analysis purposes.

Only scheduled assessments will be included in the summary tables, which are presented by visit. All assessments (including both scheduled and unscheduled) will be presented in the data listings and figures.

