4.3. Definition of Baseline Values and Study Day

Unless otherwise specified, the baseline value for each parameter is defined as the value collected at the time closest to, but prior to, the start of DTX101 administration. The documented history or measurement before Day 0 following the appropriate washout will be used for the baseline values of FIX. For assessments on or after Day 0, the study day will be calculated as assessment date minus date of DTX101 injection (Day 0). For assessments prior to Day 0, the study day will be calculated as the assessment date minus

date of DTX101 injection (Day 0). Study start date is defined as the date the informed consent form (ICF) is signed.

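### The by-dose FIX time course and mixed model in SAP Section 11 have no rule for samples that contain infused factor IX

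*SAP*

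**What the plan says.** **Analysis.** SAP Section 11 (Pharmacodynamics) lists FIX activity per subject, then says "FIX activity will be summarized by dosage at each scheduled time point". It continues: "The association between FIX activity and dose will be evaluated by a linear mixed-effects regression model adjusted for potential confounders". The confounders are not named.

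**Filters.** SAP Section 4.2 says "Only scheduled assessments will be included in the summary tables, which are presented by visit", which separates scheduled from unscheduled samples and nothing else. Section 4.1 rules out imputation of missing values. Section 4.3 is the only SAP analysis rule for FIX that mentions washout, and it concerns baseline: "The documented history or measurement before Day 0 following the appropriate washout will be used for the baseline values of FIX".

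**Permitted FIX.** After any screening washout, "subjects can transition back on to their prophylactic regimen until the protocol mandated washout period prior to the Week 6" assessment (Protocol Figure 3–2, note b). Under Protocol Section 3.2.3.2 that washout starts at Week 3 for long-acting and Week 5 for traditional FIX. Its stated reason is "In order to accurately assess vector-derived FIX activity as a result of DTX101 infusion", tied to the Week 6 measurement. For later prophylaxis the same section provides: "If a subject resumes prophylactic FIX replacement therapy, as rescue treatment after Week 6, additional washout periods prior to Week 24 and Week 52". It also says: "The on-demand use of recombinant FIX is not prohibited and may be used at any time during the study".

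**The concern.** A clotting assay on a sample drawn after a FIX infusion reads infused and vector-derived factor together. The protocol recognises this at Week 6, and at Weeks 24 and 52 for subjects back on prophylaxis. The SAP recognises it at baseline. Neither document carries the principle into the analysis of the other scheduled visits.

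A secondary objective is to describe how FIX activity develops at each dose, how high it goes and how long it lasts. The subject whose expression is low or lost is the one most likely to be bleeding and receiving FIX, so infused factor could look like sustained expression. In a cohort of three, he supplies one third of each by-dose mean.

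**Working it through.** The plan gives no figure to reproduce. The check counts which scheduled samples the protocol protects, then asks what inclusion and exclusion do to a small-cohort mean.

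**1. Scheduled post-dose FIX samples** (Protocol Table 15–1 and footnote a). Weeks 2, 4, 6, 8, 10, 12; every 4 weeks from 16 to 48 (nine visits); Week 52. Total 6 + 9 + 1 = 16. A prophylaxis washout is timed to three of them: Weeks 6, 24 and 52.

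**2. Affected samples.** A sample counts as affected if drawn on prophylaxis, or less than 7 days (traditional) or 21 days (long-acting) after it stops. These are the protocol's own washout lengths.

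- Entry prophylaxis: Weeks 2 and 4. For long-acting FIX, Week 4 is only one week after the Week 3 stop.
- Rescue: visits after the rescue week, except Weeks 24 and 52. Assumed: prophylaxis restarts directly after Week 24.

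| Rescue starts (assumed) | Affected visits after Week 6 | Entered on prophylaxis | Entered on-demand |
|---|---|---|---|
| No rescue | none | 2 of 16 | 0 of 16 |
| Week 8 | 10, 12, 16, 20, 28–48 (10) | 12 of 16 | 10 of 16 |
| Week 12 | 16, 20, 28–48 (8) | 10 of 16 | 8 of 16 |
| Week 24 | 28–48 (6) | 8 of 16 | 6 of 16 |
| Week 36 | 40, 44, 48 (3) | 5 of 16 | 3 of 16 |

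The counts are the same for both products, because no scheduled visit falls between Weeks 21 and 24 or between Weeks 49 and 52. Rescue before the Week 8 sample would give 11 visits after Week 6, so at most 13 of 16.

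**3. On-demand doses.** No visit is protected from these. If a dose falls on a random day of a 28-day visit interval, the chance that the next sample lies within the washout length is 7/28 = 25% (traditional) or 21/28 = 75% (long-acting).

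**4. Effect on a mean of three.** Let v be the affected subject's vector level, x his reading, and m the mean of the other two. The true mean is (v + 2m)/3.

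- All samples: error = (x − v)/3.
- Subject excluded: error = m − (v + 2m)/3 = (m − v)/3.

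With assumed v = 2% and m = 10%, the true mean is (2 + 20)/3 = 7.3%.

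| Reading x (assumed) | All samples | Subject excluded |
|---|---|---|
| 4% | 24/3 = 8.0% | 10.0% |
| 10% | 30/3 = 10.0% | 10.0% |
| 40% | 60/3 = 20.0% | 10.0% |

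Both means lie above the truth. Inclusion is closer when x is between 2% and 10%, and exclusion is closer above 10%. Neither summary suffices alone.

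**5. Would a strict cut-off drop compliant samples?** Visit windows are ±2 days (Week 6), ±4 (Week 24) and ±7 (Week 52). If washout starts on the nominal date, the earliest permitted sample comes:

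- traditional: 7 − 2 = 5, 7 − 4 = 3 and 7 − 7 = 0 days after it starts;
- long-acting: 21 − 2 = 19, 21 − 4 = 17 and 21 − 7 = 14 days.

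A bare 7- or 21-day rule could therefore discard protocol-compliant samples at the three best time points.

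**6. Other SAP provisions.** The per-protocol set (Section 4.6.3) removes subjects with significant deviations or too few FIX samples. Permitted FIX use is not a deviation, and Section 8 specifies that set only for the primary efficacy endpoint.

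**The case against.** **The objective is plasma FIX activity.** The secondary objective does not say vector-derived, and the stated purpose of the washout is tied to Week 6. This stands in part: the protocol never promises vector-only readings at every visit, so the all-samples summary is legitimate and should stay. It cannot by itself show duration or magnitude by dose after gene transfer.

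**The model or shells may handle it.** The unnamed confounders could include recent FIX use, and SAP Section 4.1 refers to table shells that are not supplied. Neither can be ruled out. But a covariate would leave the by-visit summary unchanged, and the listings and figures in Section 11 are not described as marking such samples.

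**Exclusion has its own bias.** This stands, as step 4 shows. Flagging on-demand doses also removes bleeders' samples selectively. Hence both versions are needed, for the summary and for the model.

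**The size rests on assumptions.** Also true. Without rescue, and apart from on-demand doses, a subject who enters on prophylaxis has 2 affected visits. The 40% reading is illustrative, with no source in the documents.

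**Stronger readings to avoid.** A reader might infer that the annualized bleeding rate and FIX use are invalid because they combine time on and off prophylaxis. The documents do not support that. Their objectives concern bleeds and replacement therapy during the study, and totals through Week 52 answer them. The direction of any effect on the bleeding rate is unclear: bleeds that led to rescue count, and later ones may be suppressed. A reader might also infer that the Week 6 endpoint or dose selection is compromised. A prophylaxis washout precedes that measurement, and SAP Section 3.1.2 models dose-efficacy on the vector-derived level at 6 weeks, so this point makes no claim there.

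**Conclusion.** The concern holds for the secondary FIX time course and the mixed model. Followed as written, SAP Section 11 combines infused with vector-derived factor at 2 of 16 post-dose visits for a subject who enters on prophylaxis. That becomes 10 of 16 if he is also rescued at Week 12 (5 to 12 for rescue between Week 36 and Week 8), or 8 of 16 for a rescued subject who entered on-demand. Visits soon after on-demand doses add to this.

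The visit and washout counts follow from the documents. The number of subjects on prophylaxis or rescued, the rescue dates, the day of on-demand dosing and the FIX levels in the example are assumptions. The direction is upward in both summaries when the affected subject's vector level is below the others', but which is closer to the truth depends on his reading.

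The endpoint is secondary and largely descriptive. This should be fixed before database lock, because exclusions chosen after the data are seen would be data-driven.

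**What to change.** In SAP Section 11:

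1. **Flag.** From recorded infusion dates, mark each FIX sample drawn within 7 days (traditional) or 21 days (long-acting) after any exogenous FIX, prophylactic or on-demand.
2. **Protect the washed-out visits.** At Weeks 6, 24 and 52, keep a sample taken after a protocol washout and within the visit window, even if a few days short, and show the actual days since last FIX. An on-demand dose during that washout still flags the sample.
3. **Report both ways.** Present the by-dose summary and the mixed model with all samples and with unflagged samples only. Name Weeks 6, 24 and 52 as the main vector-derived time points.
4. **Show the numbers.** Give, by dose and visit, the number of samples flagged and of subjects on rescue. Mark flagged samples in the listings and figures.

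As a supplementary display only, show the bleeding rate and FIX use also from Week 6 to Week 52, with the number of subjects and days on prophylaxis by dose. Day 0 to Week 52 totals stay as planned. The extra window helps because, at the 2 to 3 infusions per week cited in Protocol Section 1, traditional prophylaxis to Week 5 contributes 10 to 15 infusions even if the subject needs none afterwards.

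**Cost.** About a page of SAP text and a few tables; no new visits or samples. Protocol Section 6.4 already requires drug name, dates and reason for use, which is what the flag needs. No protocol wording change is needed for this fix.

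**Downside.** The unflagged summary has fewer samples: none at Weeks 2 and 4 if a whole cohort enters on prophylaxis, and 2 of 3 at eight later visits if one subject is rescued at Week 12. Exclusion can favour responders, and the SAP should say so.

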3.1 Study Overview

Study 101HEMB01 is a Phase I/II, open-label, single-arm, multicenter, dose-finding safety study to determine the safety, tolerability, and efficacy of DTX101 in adults with moderate/severe to severe hemophilia B. The primary objectives of the study are to determine the safety of single ascending IV doses of DTX101 and to identify the OBD of DTX101 that either achieves or is the closest to achieving the target peak FIX activity of $\geq 20\%$ of normal.

Eligible subjects will receive a single IV infusion of DTX101. Subjects will be dosed sequentially in cohorts with a minimum of 3 subjects each. Dose escalation will be conducted according to a model that uses safety and efficacy data to predict the OBD ([Section 10.5.1](#)).

The following candidate doses (per kg of body weight) will be used to identify the OBD:

- **Dose 1:** 1.6×10^{12} GC/kg
- **Dose 2:** 3.0×10^{12} GC/kg
- **Dose 3:** 5.0×10^{12} GC/kg
- **Dose 4:** 1.0×10^{13} GC/kg

There will be a minimum of 7 days between dosing of each subject within a cohort and a minimum of 42 days between the dosing of the last subject in one dosing cohort and the first subject in the next dosing cohort. The recommendation to proceed to the next dose cohort will be made by the DSMC ([Section 9.3](#)) after evaluation of the safety data for all subjects in a dosing cohort after they have completed Week 6, as outlined in the DSMC charter. There will be no intra cohort dose escalations.

Study enrollment will be suspended if any of the safety stopping criteria are met ([Section 3.2.4](#)).

Subjects will be followed for 52 weeks after dosing. After completion of this study, subjects will be offered enrollment in an extension study to evaluate the long-term safety and effect of DTX101 on clinical outcome measures.

[figure not shown]

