10.5.8 Interim Analysis

An interim analysis will be conducted when the last subject dosed completes Week 6 of the study. The purpose of this interim analysis is to determine FIX activity in all cohorts to determine the OBD of DTX101 and provide an initial safety and efficacy assessment of DTX101. Results and their dissemination will be at the sponsor's discretion. Any interim analyses conducted will not bias the conduct of the study. A detailed plan for the analysis of the safety and efficacy data will be presented in the SAP.

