4.4. Sample Size

The study is expected to enroll 3 cohorts of 3 subjects and additional 3 subjects at the OBD for a total of 12 subjects. The maximum of subjects to be enrolled is 18. This sample size consideration is consistent with the sample size of other study with similar design.

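### Interim by-dose TEAE percentages pool unequal follow-up tied to dosing order; SAP Section 13 needs a common Week 6 window and exposure-adjusted rates alongside the cumulative tables

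*SAP*

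**What the plan says.** The protocol (Section 10.5.8) sets the timing: "An interim analysis will be conducted when the last subject dosed completes Week 6 of the study". The purpose is to determine the OBD and to "provide an initial safety and efficacy assessment of DTX101". It promises a detailed plan in the SAP.

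SAP Section 13 is two sentences. The first gives the timing ("An interim analysis will be conducted after week 6 FIX activity results are available for all enrolled subjects") and the second the content ("All tables/listings/figures for the full analysis will be produced for interim analysis"). It sets no data cut-off common to all subjects and defines no interim version of any endpoint.

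For adverse events, SAP Section 9.1 states: "The total number, the frequency, and the percentage of subjects with TEAEs will be tabulated by dosage, SOC, and PT for the following". The list that follows includes related TEAEs and those of Grade 3 or higher. No time window or person-time denominator is given. SAP Section 8 summarizes ABR and FIX use by dose; SAP Table 2-1 defines both through Week 52.

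Dosing is sequential. Protocol Section 3.1 requires at least 7 days between subjects in a cohort and "a minimum of 42 days between the dosing of the last subject in one dosing cohort" and the first subject of the next. On size, SAP Section 4.4 says: "The study is expected to enroll 3 cohorts of 3 subjects and additional 3 subjects at the OBD for a total of 12 subjects". It adds: "The maximum of subjects to be enrolled is 18".

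**The concern.** At Week 52 every completer has about the same follow-up, so a cumulative percentage by dose is a fair display. At the interim this is not so. The first subjects, all at the lowest dose, have been followed for months, while the last subject has been followed for about six weeks. A table of subjects with at least one TEAE then reflects time at risk as well as dose, and subjects dosed later tend to look safer. TEAE incidence by dosing cohort is a primary endpoint, and this is the point at which the initial safety assessment is made.

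ABR and FIX use raise a different problem. Dividing by time removes the effect of length in expectation. However, subjects on prophylaxis at entry may stay on it until Week 3 (long-acting FIX) or Week 5 (traditional FIX) and then move to on-demand treatment (Protocol Section 3.2.3.2). In a short follow-up most of the time can precede that switch; in a long one little of it does.

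**Working it through.** **The plan's own figure.** 3 cohorts × 3 + 3 at the OBD = 12, which reproduces SAP Section 4.4. The documents give no figure for follow-up at the interim, so it is derived here.

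**Calendar at minimum spacing.** Within a group, doses fall on Days 0, 7 and 14. The next group starts 42 days after the last dose, so each cycle is 14 + 42 = 56 days. The fourth group starts on Day 168 and its last subject is dosed on Day 182. The cut-off is 182 + 42 = Day 224 (Week 32), and follow-up is (224 − dosing day)/7.

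| Group | Dosing days | Follow-up (weeks) |
|---|---|---|
| 1 | 0, 7, 14 | 32, 31, 30 |
| 2 | 56, 63, 70 | 24, 23, 22 |
| 3 | 112, 119, 126 | 16, 15, 14 |
| 4 | 168, 175, 182 | 8, 7, 6 |

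Mean follow-up in the first and last groups is 31 and 7 weeks, a ratio of 4.4. Waiting for the assay result, as the SAP does, adds the same interval to everyone.

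**Other structures.** The last group has 6–8 weeks in each case.

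- Three groups: cut-off 126 + 42 = Day 168; Cohort 1 has 22–24 weeks.
- Two groups: cut-off 70 + 42 = Day 112; Cohort 1 has 14–16 weeks.
- Six groups (18 subjects): cut-off 294 + 42 = Day 336; Cohort 1 has 46–48 weeks.
- Four groups, with the OBD expansion only 7 days after Cohort 3: last dose Day 147, cut-off Day 189; Cohort 1 has 25–27 weeks.

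For a given structure, slower accrual lengthens the earlier groups' follow-up and leaves the last subject at about 6 weeks.

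**Effect on TEAE percentages with no dose effect.** Assume one constant hazard h per week at every dose. Then P(at least one event) = 1 − exp(−h × weeks), evaluated at 31 and 7 weeks.

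| Assumed h | Cohort 1 | Last group |
|---|---|---|
| 1% | 1 − exp(−0.31) = 27% | 1 − exp(−0.07) = 7% |
| 2% | 1 − exp(−0.62) = 46% | 1 − exp(−0.14) = 13% |
| 4% | 1 − exp(−1.24) = 71% | 1 − exp(−0.28) = 24% |

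The hazards are illustrative; the documents give none.

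**ABR precision.** One bleed is 52/6 = 8.7 per year for a subject with 6 weeks and 52/30 = 1.7 for one with 30 weeks. The last group contributes 21/52 = 0.40 person-years and Cohort 1 contributes 93/52 = 1.79. At an assumed true ABR of 4, the Poisson standard error, √(rate/person-years), is √(4/0.40) ≈ 3.1 versus √(4/1.79) ≈ 1.5.

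**Pre-washout share of follow-up, subjects on prophylaxis at entry.** In the last group it runs from 3/8 = 38% (long-acting, 8 weeks) to 5/6 = 83% (traditional, 6 weeks). In Cohort 1 it runs from 3/32 = 9% to 5/30 = 17%.

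**The case against.** The strongest reply is that the OBD does not come from these tables. It is the dose that minimizes the Euclidean distance in the bivariate CRM (SAP Section 3.1.1), and Protocol Section 10.5.1 models outcomes in the first 6 weeks, which every followed subject has completed by then. This stands. A reader might infer that unequal follow-up biases the OBD choice, but the documents show no route from a cumulative TEAE percentage to the model. One caution is that the DLT definition in SAP Section 3.1.2 repeats no window, so this reassurance rests on the protocol's wording.

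Other objections also hold in part:

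- **Dose order.** A reader might infer that the highest dose is always the one favoured. Only Cohort 1's dose is fixed. De-escalation and intermediate doses are allowed, and the last three subjects are planned at the OBD. If the OBD were Cohort 2's dose, that dose group would pool 22–24 and 6–8 weeks. The confounding is with dosing order, not strictly with dose level.
- **Event timing.** The constant hazard is an assumption. Infusion reactions and early ALT rises fall largely in time that all subjects share, which shrinks the gap. It need not vanish, because adverse events are collected until study exit.
- **FIX use.** The 83% is the extreme for traditional-FIX users, and on-demand subjects are also eligible. Protocol Section 8.1.3 describes recording on-demand use; whether prophylaxis enters the annualized figure is not stated.
- **Existing safeguards.** Duration of participation is summarized by dose (SAP Section 7.2), TEAEs are listed, and the summaries are descriptive. These make the imbalance visible but do not adjust the percentages for it.

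**Conclusion.** The point holds for the interim by-dose TEAE tables. They are confounded with follow-up time and tend to favour later-dosed subjects. Under the expected 12-subject plan at minimum spacing, follow-up is 30–32 weeks in Cohort 1 and 6–8 in the last group. Under the assumed equal hazards, that alone separates them by 27% vs 7% up to 71% vs 24%. The size depends on the number of groups, the gap before the expansion and the timing of events.

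Two stronger readings are not supported. The first is that all early cohorts have at least 30 weeks: on this calendar only Cohort 1 does, and only if there are four groups each 42 days apart (or more groups or slower accrual). The second is that annualized rates merely compare follow-up time: they already divide by it. Their weaknesses at the interim are imprecision, a different mix of time before and after the washout, and the lack of an interim definition. The Week 6 FIX table compares like with like and needs no change.

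**What to change.** In SAP Section 13, keep the cumulative TEAE tables and add:

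- by-dose tables of TEAEs, related TEAEs and TEAEs of Grade 3 or higher, restricted to Day 0 through Week 6, the window all followed subjects share;
- events per subject-week of follow-up by dose, for the full period;
- median and range of follow-up per dose in the table headers.

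Label interim ABR and annualized FIX use as preliminary. Show them with person-time and separately before and after the start of the Week 6 washout, or give subject listings only.

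The Week 6 tables should add to the cumulative ones, not replace them. A cut at Week 6 alone would drop later events from the by-dose summaries, including some inside the 8-week ALT window of Protocol Section 3.2.4.

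The cost is a short SAP revision, a date cut-off in existing programs and a few extra interim tables. No additional data are needed.
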